**A Multicenter Randomized Clinical Trial of 4 vs. 8 Days of Definitive
Antibiotic Therapy for Early Ventilator-Associated Pneumonia in the
Surgical Intensive Care Unit:**

The Duration of Antibiotic Therapy for Early VAP (DATE) Trial

(COMIRB 13-3062, NCT01994980)

12.26.13

[name]

[name]

[name]

[name]

[name]

[name]

[name]

[name]

[name]

[name]

Departments of Surgery, Medicine, Division of Infectious Disease, and Pharmacy

Denver Health Medical Center/University of Colorado Health Sciences Center

Background:

The prevalence of multi-drug resistant (MDR) pathogens in intensive care units (ICUs) worldwide has reached epidemic proportions [1, 2]. In some cases, the choice of potential therapy is limited or even non-existent [3]. Antibiotic prescription, through selection pressure, represents the main mechanism by which resistance emerges [4]. Limitations in the development of new antibiotics [5] underscores the importance of adherence to the principles of antibiotic stewardship [6].

Ventilator associated pneumonia (VAP) is the most common serious infection in mechanically ventilated, critically ill patients [7]. Approximately one half of antibiotic prescription in the ICU is related to VAP, including prophylactic, empiric, and definitive therapy [8]. The development of evidence-based algorithms for the rational use of antibiotics in the management of patients with both suspected and confirmed VAP is pivotal to decreasing the emergence of MDR pathogens.

Shortening the duration of antimicrobial therapy for VAP represents one strategy to curtail the emergence of MDR pathogens. Although current guidelines recommend a treatment course of 8-14 days [9], both clinical and microbiologic resolution (MR) of infection typically occur much sooner [10, 11]. In one study of ICU patients ventilated for > 5 days who developed VAP, 8 days of antimicrobial therapy was equally as effective as 15 days, provided VAP was not caused by a non-lactose fermenting gram negative bacillus [12]. Favorable results following courses of therapy < 8 days have been reported, albeit in small, uncontrolled series [13].

One subset of patients for whom a decreased duration of antimicrobial therapy may be particularly effective is those who develop VAP \leq 7 days after intubation (early VAP). Early VAP comprises the majority of cases of pneumonia diagnosed in the ICU[14] . Furthermore, as compared to patients who develop late VAP, patients who develop early VAP are more likely to be infected with community-acquired pathogens sensitive to narrow spectrum antibiotics [14]. Finally, nearly all cases of

early VAP caused by sensitive pathogens demonstrate MR after relatively short (3-5 days) courses of therapy [10].

The hypothesis of this randomized clinical trial (RCT) is that 4 days of antibiotic therapy, as compared to 8 days, is equally effective and results in decreased antibiotic exposure among surgical ICU patients with early VAP.

Methods:

Study Design: Randomized, double-blind (until treatment day 5) clinical trial.

Intervention: Default 4 vs. 8 days of antibiotic therapy.

Screening Pool: Trauma-Surgical ICUs.

Inclusion Criteria:

- 1) Surgical patient
- 2) Early VAP, defined as:
 - a. Duration of Intubation: 2-7 days [9] (via endotracheal or tracheostomy tube).

- b. Clinical suspicion of pneumonia: New or progressing infiltrate on chest radiograph (CXR) along with ≥ 1 of the following: Temperature $\geq 38.5^{\circ}\text{C}$ or $< 36.5^{\circ}\text{C}$; blood leukocytes $>11,000 \text{ mm}^3$ or $<4,000 \text{ mm}^3$; purulent tracheal secretions; or $\text{PaO}_2:\text{FiO}_2 < 200$ [15].
- c. Quantitative microbiologic confirmation: Bronchoalveolar lavage (BAL) culture showing $\geq 10^5 \text{ cfu/mL}$ of at least one pathogen [16]. The quantitative microbiology threshold will be lowered to $\geq 10^4 \text{ cfu/mL}$ if the patient was being treated with antibiotics to which the pathogen is sensitive at the time of the BAL.

3) Hospital LOS ≤ 10 days at the time that the BAL was obtained.

Exclusion Criteria:

- 1) Age < 18 years.
- 2) Prior episode of VAP for the index admission (the patient may have had prior BALs sent for culture, but these cannot have met the above mentioned diagnostic criteria for VAP).
- 3) VAP caused by a MDR pathogen: Early VAP is rarely caused by MDR pathogens; in a recent analysis of our surgical ICU, 94% of cases of early VAP were caused by highly sensitive pathogens (Methicillin-sensitive staphylococcus aureus 39%, Haemophilus influenza 35%, Streptococcus pneumoniae 16%, Esterichia coli 9%) [14]. Patients with early VAP caused by the following MDR pathogens will be excluded: Methicillin-resistant Staphylococcus aureus (MRSA), Vancomycin-intermediate Staphylococcus aureus (VISA), pseudomonas aeruginosa, Vancomycin-resistant enterococcus (VRE), Acinetobacter baumannii, Stenotrophomonas maltophilia, carbapenem-

resistant enterobacteriaceae (CRE), and extended-spectrum beta lactamase producing gram negative bacilli.

- 4) Causative pathogen not sensitive to choice of initial empiric antibiotic.
- 5) Antibiotic therapy for ≥ 5 of the last 10 days preceding the BAL.
- 6) Septic shock, defined as evidence of tissue hypoperfusion after adequate volume expansion, due to infection, and requiring ≥ 1 vasopressor [17].
- 7) Current or recent (within 30 days) use of immunosuppressive medications.
- 8) Length of stay ≥ 72 hours in a transferring facility.
- 9) Pregnancy or lactation.
- 10) Legal arrest or incarceration.
- 11) Moribund state in which death is imminent.

Outcomes:

The two main outcomes will be effectiveness of treatment and antibiotic exposure.

Effectiveness of treatment will be assessed in three ways: 1) Clinical response, 2) MR, and 3) biomarker response.

Clinical Response: Current guidelines state that appropriately treated patients with VAP should have a favorable clinical response by day 3, and a substantial improvement by day 6 [9]. Clinical variables used to assess for treatment response are organized into the Clinical Pulmonary Infection Score (CPIS). The original CPIS, as described by Pugin et al. [18], included five clinical variables [temperature, white blood

cell count (WBC), tracheal secretions, ratio of P_aO_2 to F_iO_2 (P:F), and chest radiograph findings) and one microbiologic variable (culture of tracheal aspirate and its relationship to the gram stain). Several authors have since modified the score to exclude the microbiologic variable in order to both screen for VAP and monitor efficacy of treatment [11, 19]. This modified score, herein referred to as CPIS_{clinical}, omits the microbiologic variable and ranges from 0-10.

The CPIS_{clinical} will be calculated at baseline and daily thereafter during the study period. In the case that certain individual variables are not available for abstraction, they will be left blank rather than obtained solely for the purpose of the study. The worst values (those associated with the highest number of points) for each variable over the 24 hours prior to the BAL will be used. Tracheal secretions will be scored based on daily progress notes from the respiratory therapist. Chest radiograph findings will be scored based on attending final radiologist reads.

It is important to note that CPIS_{clinical} possesses limited accuracy for monitoring VAP resolution in surgical ICU patients [20, 21]. Furthermore, a multicenter RCT reported decreased organ failure, mortality, and antibiotic use for patients with suspected VAP managed using a microbiologic endpoint as compared to a clinical one [22]. For these reasons, efficacy of treatment will also be assessed both microbiologically and using a biomarker of infection (*see below*).

Microbiologic Response: The definition of microbiologic response for VAP reported most commonly ranges from $<10^2$ cfu/mL [23] to $<10^3$ cfu/mL [10] from a repeat BAL culture obtained the day after the end of therapy. For the purposes of this trial, microbiologic response will be defined as growth of the original pathogen of $<10^3$ cfu/mL from a BAL culture obtained the day after the end of treatment. Repeat BALs will thus be obtained on day 5 for the 4-days of antibiotics group and day 9 for the 8 days of antibiotics group. If the patient is no longer intubated at this time, a repeat BAL will not be obtained and MR will be inferred. The treatment team will have access to the results of the repeat BAL.

Biomarker Response: Circulating levels of calcitonin precursors, including procalcitonin, are elevated in bacterial infections [24, 25]. Normalization of procalcitonin concentration in patients receiving therapy for VAP has been shown to both correlate with clinical response and guide discontinuation of antibiotics [26]. The relationship between clinical response, MR, and procalcitonin concentration has not been evaluated prospectively in critically ill patients being treated for VAP and will be the focus of a sub-analysis.

Currently, procalcitonin concentration is measured in all surgical ICU patients for whom a BAL is sent on the day of the BAL as part of a separate non-interventional study. For the purposes of the current trial, procalcitonin concentration will also be measured during treatment in order to assess response, as well as following treatment in order to assess for recurrence. Because study entry will occur at the time that VAP is confirmed microbiologically (approximately 72 hours following the BAL and initiation of empiric antibiotics), these measurements will begin after three days of antibiotic therapy. Procalcitonin concentration will then be measured daily for the remainder of treatment, as well as daily for 72 hours following treatment. Thus, the 4 day group will have procalcitonin concentration measured at baseline, treatment days 3 and 4, and post treatment days 1-3. The 8 day group will have procalcitonin measured at baseline, treatment days 3-8, and post-treatment days 1-3. The treatment team will have access to the results of these measurements. For the purposes of the trial, biomarker resolution will be defined as a procalcitonin concentration $< 0.5 \mu\text{g/L}$ or a decrease of $\geq 80\%$ relative to the day of the BAL [26].

Additional Outcomes: Days of antibiotics, antibiotic days (defined as the product of days of antibiotics and number of antibiotics per day), recurrence, ventilator days, empyema, need for tracheostomy, non-pulmonary infections, ICU length of stay (LOS), hospital LOS, and mortality. Recurrence is defined using the same clinical and microbiologic criteria as the initial episode of VAP, and occurring 2-14 days

following completion of initial therapy. Relapse is defined as recurrent VAP caused by the initial pathogen; super-infection is defined as recurrent VAP caused by ≥ 1 new pathogen. VAP occurring > 14 days following completion of initial therapy will be considered a second episode of pneumonia as opposed to a recurrence. The incidence of recurrent VAP due to a MDR pathogen, as well as any other infection caused by a MDR pathogen, will also be abstracted.

Baseline Variables: Age (years), gender, admission diagnosis, associated diagnoses, admission APACHE II score, comorbidity index [27], prior and current antibiotic exposure, base deficit, serum lactate concentration, time from ICU admission to BAL, presence of organisms on gram stain, and presence of polymorphonuclear lymphocytes on gram stain.

Study Flow & Stop Criteria: The trial will be reported in accordance with the recommendations of the CONSORT Statement [28]. IRB approval will be obtained. All subjects or their legally authorized representative will provide written consent for study participation. The trial is registered with the US National Institutes of Health (ClinicalTrials.gov Identifier NCT01994980).

Screening will occur daily by study personnel. Eligible patients will be approached as soon as possible after inclusion criteria are met (i.e., 1-3 days prior to randomization). Randomization will occur using a computer-generated block pattern on the morning following the fourth day of appropriate antibiotic therapy.

Empiric antibiotic therapy will be instituted as soon as possible following BAL acquisition. The default antibiotic will be ceftriaxone 2 gram IV q24 hours. Patients with potential allergies to cephalosporins will receive levofloxacin 750 mg IV q24hours. Pre-existing treatment for a non-

pulmonary infection with at least one antibiotic that has appropriate activity against the VAP pathogen may be substituted for the default antibiotic. Once sensitivity data become available (approximately 72 hours after BAL acquisition), therapy may be de-escalated to a more narrow-spectrum agent (e.g., cefazolin) as indicated.

The default duration of antibiotic therapy will be determined by study group assignment; the treatment team will be asked to adhere to study group assignment whenever possible. However, the treatment team may choose to extend the duration of antibiotic therapy based on clinical circumstances, such as deterioration in hemodynamic or respiratory status that is believed to be related to incompletely treated VAP, or continued treatment of a non-pulmonary infection. The treatment team may also decide to extend the duration of antibiotic therapy based on the results of serial procalcitonin measurements. Finally, the treatment team may decide to extend the duration of antibiotic therapy based on the results of the BAL obtained the day after completion of therapy. These clinical decisions will take precedence over study group assignment.

Patients will be followed for 28 days or until hospital discharge, whichever occurs first. Please see attached data collection tool for detailed information.

Sample acquisition and processing: The default method for BAL specimen acquisition will be via the blind or “mini” BAL technique [18], using an 85 mm by 4 mm bronchial diagnostic catheter (Combicath, ® Prodimed, Neuilly-en-Thelle, France). The catheter is passed through the artificial airway until resistance is met. It is then withdrawn approximately 1 cm and the inner lavage catheter is deployed. Lavage is then performed with 20 – 40 mL of sterile saline.

The BAL will be obtained bronchoscopically if bronchoscopy is being performed for another indication (e.g., pulmonary toilet, percutaneous dilational tracheostomy). Lavage is performed using 20-40 mL of normal saline lavage into the lobar bronchus that appears most abnormal on CXR.

Using a 0.001 calibrated loop, vortexed BAL specimens will be plated onto sheep blood, MacConkey, and Chocolate agar at 35°C - 37°C in CO₂. Plates will be examined after 24, 48, and 72 hours prior to issuing a final negative report. 100 or more colonies per plate is considered significant and represents $\geq 10^5$ cfu/mL.

Statistical Analyses:

Power analysis: Power analysis was performed using SAS Version 9.1 (SAS, Inc., Carey, NC, *proc power*). The Analysis was based on a non-inferiority study design, defined as a difference in outcomes between the 4 day and 8 day groups of < 10%. Furthermore, as the intention was to show non-inferiority, tests were one-sided using an alpha error level of 0.10. The beta error level was set at 0.20 for 80% power. Analysis for the outcome of VAP recurrence returned the largest sample size. From 2010-2012, during which time VAP was treated with ≥ 8 days of therapy, the incidence of recurrent VAP in the DHMC surgical ICU was approximately 25%. Projecting a recurrence rate after 4 days of treatment of 35% returns a total sample size of 103..

Interim Analysis: An interim analysis will be conducted for all outcomes after 50% accrual (n_{total}=50).

Data Analysis: Data analyses will be performed using SAS Version 9.1 (SAS, Inc., Carey, NC). Data will be analyzed using an intention-to-treat strategy (i.e., patients randomized to receive 4 days of antibiotic therapy will be analyzed with this group even if they receive longer courses). Data will be expressed as median (range) or number (%). Normality of continuous variables will be assessed using the

Kolmogorov-Smirnov test. Differences in the means of continuous variables that are distributed normally will be assessed using the Student's t-test. Differences in the medians of continuous variables that are not distributed normally will be assessed using the Wilcoxon Rank Test. Proportions of categorical variables will be compared using the chi-squared test. When expected cell counts are < 5, Fischer's exact test will be used. Univariate analysis of categorical outcomes will be expressed as the relative risk with 95% confidence intervals. A logistic regression model will be fit to address possible confounding by differences in baseline parameters between groups. Baseline variables associated with randomization status at the $p<0.25$ level by univariate analysis will be added to the model using a forward selection method. The overall contribution of the fitted model to predicting variability in the outcome of interest will be assessed using the likelihood ratio chi-squared test. The independent contribution of individual variables will be assessed using the Wald chi-squared test. Model fit was will be assessed using the Hosmer-Lemeshow goodness-of-fit chi-squared statistic, with $p>0.05$ indicating acceptable model calibration. The alpha error level is defined at 0.05, with statistical significance set at $p<0.05$.

Adverse Event Monitoring and Reporting: Adverse event monitoring will occur daily. The safety of the study will be monitored by an independent, external Data Safety Monitoring Board, consisting of a medical intensivist, and an infectious disease physician. The committee will meet biannually and submit written reports to the IRB.

References:

1. Edwards, J.R., K.D. Peterson, Y. Mu, S. Banerjee, K. Allen-Bridson, G. Morrell, et al., National Healthcare Safety Network (NHSN) report: data summary for 2006 through 2008, issued December 2009. *Am J Infect Control* 2009;37:783-805
2. Neu, H.C., The crisis in antibiotic resistance. *Science* 1992;257:1064-73
3. Mahgoub, S., J. Ahmed, and A.E. Glatt, Completely resistant *Acinetobacter baumannii* strains. *Infect Control Hosp Epidemiol* 2002;23:477-9
4. Kollef, M.H. and V.J. Fraser, Antibiotic resistance in the intensive care unit. *Ann Intern Med* 2001;134:298-314
5. Bradley, J.S., R. Guidos, S. Baragona, J.G. Bartlett, E. Rubinstein, G.G. Zhanel, et al., Anti-infective research and development--problems, challenges, and solutions. *Lancet Infect Dis* 2007;7:68-78

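### Microbiologic response is inferred for patients off the tube at day 5 in one arm and day 9 in the other, so extubations in between count as automatic responses almost only in the 8-day arm; biomarker resolution has no stated assessment day

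*Combined protocol and SAP*

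**What the plan says.** **Timing and inference rule.** Under Outcomes, Microbiologic Response, the combined protocol and SAP defines MR as fewer than 10^3 cfu/mL of the original pathogen on a "BAL culture obtained the day after the end of treatment". It continues: "Repeat BALs will thus be obtained on day 5 for the 4-days of antibiotics group and day 9 for the 8 days". The inference rule follows: "If the patient is no longer intubated at this time, a repeat BAL will not be obtained and MR will be inferred".

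**Randomization and extension.** Study Flow & Stop Criteria states: "Randomization will occur using a computer-generated block pattern on the morning following the fourth day of appropriate antibiotic therapy". That is about day 5. The same section lets the treatment team "extend the duration of antibiotic therapy based on the results of the BAL obtained the day after completion of therapy". Under Data Analysis, "patients randomized to receive 4 days of antibiotic therapy will be analyzed with this group even if they receive longer courses".

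**Biomarker.** Resolution is procalcitonin below 0.5 ug/L or a fall of at least 80% from the day of the BAL. No day is attached. On sampling, Biomarker Response says that "procalcitonin concentration will also be measured during treatment in order to assess response, as well as following treatment in order to assess for recurrence", and "Procalcitonin concentration will then be measured daily for the remainder of treatment, as well as daily for 72 hours following treatment".

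**Role.** MR and biomarker response are two of the three ways in which effectiveness, a main outcome, is assessed. The statistical section gives no common time point for either and no sensitivity analysis for inferred MR.

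**The concern.** Judging MR the day after therapy ends is a deliberate convention and is not disputed. The difficulty is the inference rule attached to it. Patients already extubated at randomization should be balanced between arms, and inferring MR for them treats the arms alike. Patients extubated after the day-5 culture and before day 9 are not treated alike. In the 4-day arm they have a culture result, which may be positive. In the 8-day arm the same patients are responders without a culture. An MR difference therefore mixes any treatment effect with the arms' unequal chances of being scored without a culture.

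The rule is also silent on a patient who dies before the repeat BAL. Read literally, such a patient is no longer intubated.

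For the biomarker, a threshold without a day leaves the comparison open to choice after data are seen, and the plan includes an interim look at all outcomes at 50% accrual. The number of chances to meet the threshold also differs by arm.

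**Working it through.** The plan states no MR rate, extubation rate or MR-specific test, so there is no figure of its own to reproduce. Its total of 103 was set on recurrence and serves here only as a sample size.

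**Inputs from the documents:** repeat BAL on day 5 or day 9; randomization at about day 5; N = 103 (taken as 51 and 52), a 10-point margin and one-sided alpha 0.10 (Power analysis). The Background says that almost all early VAP from sensitive pathogens clears after 3-5 days of therapy; I read that as 90-95%.

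**Assumed:** e = share extubated by day 5; s = share extubated on days 5-9; p4, p8 = clearance by arm, the same in extubated and intubated patients; no deaths unless stated.

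**1. General form.**
- 4-day MR = e + (1 - e) x p4
- 8-day MR = e + s + (1 - e - s) x p8
- Observed difference = s x (1 - p8) + (1 - e) x d, where d = p8 - p4
- Shift from the true difference = s x (1 - p8) - e x d

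**2. Identical arms (d = 0).** The artefact is s x (1 - p), in favour of 8 days:
- 0.10 x 0.05 = 0.5 points
- 0.20 x 0.10 = 2 points
- 0.40 x 0.10 = 4 points

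**3. Chance of showing non-inferiority on MR, if it were tested that way** (unpooled SE). The second column has e = 0, so 4-day MR is 90%. The third has e = 20%, so 4-day MR is 0.20 + 0.80 x 0.90 = 92%.

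| Artefact | e = 0 | e = 20% |
|---|---|---|
| 0 | 66% | 72% |
| 0.5 points | 63% | - |
| 2 points | 55% | 62% |
| 4 points | 44% | - |

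**4. Arms that differ by 10 points.** With e = 10-30%, s = 10-40% and p8 = 90-95%, the extremes are:
- e = 0.30, s = 0.10, p8 = 0.95, p4 = 0.85: shift 0.005 - 0.030 = -2.5 points. Observed 89.5% against 97.0%, a gap of 7.5. Chance of wrongly declaring non-inferiority 22%.
- e = 0.10, s = 0.40, p8 = 0.90, p4 = 0.80: shift 0.040 - 0.010 = +3.0 points. Observed 82.0% against 95.0%, a gap of 13. Chance 4%.

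The intended error at the margin is 10%.

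**5. Deaths.** Take identical arms with 15% extubated by day 5, 20% extubated on days 5-9, 5% dying on days 5-9, 60% staying intubated, and 90% clearance. The 4-day arm is cultured on day 5, before these deaths, so its MR is 0.15 + 0.85 x 0.90 = 91.5%. The 8-day figure depends on the unstated rule:
- deaths inferred as responses: 0.15 + 0.20 + 0.05 + 0.60 x 0.90 = 94.0%
- deaths before culture as non-response: 0.15 + 0.20 + 0.60 x 0.90 = 89.0%

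The gap moves from +2.5 to -2.5 points on that choice alone. Counting every death by day 9 as non-response in both arms gives 0.15 + 0.80 x 0.90 = 87.0% against 89.0%. It does so by overriding 51 x 0.05 x 0.90 = 2.3 cleared day-5 cultures.

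**6. Procalcitonin days under assigned durations.**
- 4-day arm: days 3, 4 on treatment, then 5, 6, 7 (5 values)
- 8-day arm: days 3-8 on treatment, then 9, 10, 11 (9 values)

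On treatment that is 2 values against 6, and both 4-day values precede randomization. The last day scheduled in both arms is day 7. The effect in points cannot be derived from the documents.

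**The case against.** **Size.** Every rate is assumed. The Background points to high clearance, and the inclusion criteria count a tracheostomy tube as intubation, so fewer patients may leave the rule's reach by day 9. Both push the artefact down. This stands, and is why the lower half of 0.5-4 points is more likely. A reader might take clearance of 60-80% with 40% extubated and reach 8-16 points (0.40 x 0.20 to 0.40 x 0.40). The Background's expectation does not support that.

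**Test.** The plan sizes the trial on recurrence, and Data Analysis specifies chi-squared tests at 0.05. The non-inferiority probabilities are therefore illustrations, and 22% and 4% come from corner combinations. This stands.

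**Exceptions.** In the 4-day arm, a patient extubated on day 5 before the BAL, or one whose course is extended and whose BAL follows the later end of treatment, could also be inferred a responder. Hence 'almost only'.

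**Which culture counts.** A reader might infer two competing rules. The text does not go that far: it derives days 5 and 9 from the end-of-treatment definition for default courses. What is missing is a sentence for extended courses, including those extended because of the repeat BAL itself.

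**Regrowth.** A reader might add that a day-5 culture cannot show regrowth after stopping. That follows from the accepted convention, and recurrence 2-14 days after therapy is a separate outcome.

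**Biomarker.** Study Flow refers to an attached data collection tool that is not in the supplied text. It may name a day.

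**Conclusion.** The asymmetry is in the plan's own wording and the statistical section does not correct it. With identical arms it favours 8 days by about 0.5 to 4 points, for an assumed 10-40% extubated on days 5-9 and 90-95% clearance.

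A reader might infer that the rule always works against the 4-day arm, or that it undermines the trial's design. Neither follows. When the arms truly differ, inference in both also dilutes the difference; under the assumed ranges the shift runs from -2.5 to +3.0 points for a 10-point deficit. The sample size rests on recurrence and does not change. What does follow is that an MR difference cannot be read as a treatment effect without knowing how much of it is inferred.

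Confidence is high on the MR rule and moderate on the biomarker, because of the unsupplied tool. This should be fixed, preferably before the interim analysis.

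**What to change.** Analysis definitions only:

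1. Report by arm the numbers with cultured response, inferred response, cultured non-response and death before culture. Add a cultured-only sensitivity analysis, and base no between-arm conclusion on inferred MR alone.
2. Do not count a death before the repeat BAL as inferred MR; show it as its own category. Use death by day 9 as non-response in both arms only as a labelled sensitivity analysis, because it overrides completed day-5 cultures and makes MR a composite with mortality.
3. Unless the data collection tool already names a day, compare procalcitonin resolution on one common day from the start of therapy. Day 7 is the last scheduled in both arms, and it stays within the schedule for extended courses because sampling runs through treatment plus 72 hours. Handle deaths and early discharges identically in each arm.
4. For extended courses, reconcile the end-of-treatment definition with the fixed days 5 and 9, and state which culture is the MR result.

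**Cost.** A few sentences and one table; no new samples.

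**Downsides.** Item 1 exposes the artefact but does not remove it. The cultured-only set is selected: if patients extubated on days 5-9 (20%) clear at 95% and those staying intubated (60%) at 88%, the 4-day arm shows (0.20 x 0.95 + 0.60 x 0.88) / 0.80 = 89.75% against 88%, about 1.8 points in its favour. Culture days still differ: if clearance rises from 90% to 95% between days 5 and 9 with 60% still intubated, that is 0.60 x 0.05 = 3 points. Day 7 is on treatment in one arm and post-treatment day 3 in the other.

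### Inferring microbiologic response from absence of the tube alone counts withdrawal-of-care extubation, and possibly death, as a response, mainly in the 8-day arm if BALs keep to schedule

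*Combined protocol and SAP*

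**What the plan says.** Under Outcomes, MR is one of three effectiveness measures: "Effectiveness of treatment will be assessed in three ways: 1) Clinical response, 2) MR, and 3) biomarker response". The Microbiologic Response paragraph defines it as growth of the original pathogen below 10^3 cfu/mL "from a BAL culture obtained the day after the end of treatment", and fixes the days: "Repeat BALs will thus be obtained on day 5 for the 4-days of antibiotics group and day 9 for the 8 days of antibiotics group". It then adds: "If the patient is no longer intubated at this time, a repeat BAL will not be obtained and MR will be inferred".

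Study Flow & Stop Criteria sets the start of the comparison: "Randomization will occur using a computer-generated block pattern on the morning following the fourth day of appropriate antibiotic therapy". Study Design agrees: "Randomized, double-blind (until treatment day 5) clinical trial". The same Study Flow section lets the treatment team extend therapy in either arm.

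Mortality is listed under Additional Outcomes and is not linked to MR. Exclusion criterion 11, "Moribund state in which death is imminent", acts at entry. Data Analysis states: "Data will be analyzed using an intention-to-treat strategy", and explains this as analysis by assigned group even when a longer course is given.

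**The concern.** The inference makes sense for a patient whose airway was removed because the lungs improved. The rule is wider than that. It does not require the patient to be alive, does not ask why the tube came out, and makes no exception for withdrawal of life support. No other section narrows it.

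Two things are at stake. First, an effectiveness measure can record a very poor outcome as a success and so move against mortality. Second, the arms are exposed unequally. The 4-day arm is assessed on the day of randomization and the 8-day arm about four days later, so on the scheduled days the extra responses go mainly to the 8-day arm. That works against showing 4 days to be non-inferior and could hide a true result.

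**Working it through.** **Own figure.** The plan gives no figure for this rule and no mortality for days 5 to 9. The stated total of 103 is used only for arm size: 103/2 = 51.5, assuming 1:1 allocation. It does not reproduce as a two-arm total (25% versus 35%, one-sided alpha 0.10 and 80% power needs 378), but that is a separate matter. The percentage-point results below do not depend on it.

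**Timeline.** Randomization is on the morning of day 5. From there to the MR assessment is 5 − 5 = about 0 days in the 4-day arm and 9 − 5 = about 4 days in the 8-day arm. Patients who die before day 5 are never randomized.

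**Assumptions.** The daily hazard h of death or withdrawal-of-care extubation is constant and equal in both arms. The gap to the BAL is 4 days (8-day arm) or 6 hours, 0.25 day (4-day arm). MR among the remaining patients, p, is 70% to 90%. The literal rule is taken to cover deaths as well.

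**Formulas.**
- Share affected in the 8-day arm: s = 1 − (1 − h)^4; in the 4-day arm: 1 − (1 − h)^0.25. Patients = share × 51.5.
- Inflation of 8-day MR compared with scoring the events as failures: s.
- Inflation compared with leaving them out: the rule gives p(1 − s) + s = p + s(1 − p), so the excess is s(1 − p).

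| h per day | s, 8-day arm | Patients, 8-day | Patients, 4-day | Points vs failure | Points vs left out (p = 90% to 70%) |
|---|---|---|---|---|---|
| 0.25% | 1.0% | 0.5 | 0.03 | 1.0 | 0.1 to 0.3 |
| 0.5% | 2.0% | 1.0 | 0.06 | 2.0 | 0.2 to 0.6 |
| 1% | 3.9% | 2.0 | 0.13 | 3.9 | 0.4 to 1.2 |
| 2% | 7.8% | 4.0 | 0.26 | 7.8 | 0.8 to 2.3 |

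About 94% of the events fall in the 8-day arm (for h = 2%: 4.0/(4.0 + 0.26) = 0.94). The yardstick is the 10-point margin in the power analysis.

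**What simple failure scoring would do.** If death or withdrawal before each arm's own BAL counts as non-response, 8-day MR becomes p(1 − s), a fall of p × s: from 0.7 × 1.0 = 0.7 to 0.9 × 7.8 = 7.0 points. The 4-day arm falls by at most about 0.9 × (0.26/51.5) = 0.5 point. The same unequal windows now favour the 4-day arm.

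**The case against.** The strongest reply is that the sentence concerns living patients who no longer have an airway through which to lavage. It never mentions death, and a patient who dies on the ventilator was not extubated. This stands in part. A reader might infer that the plan scores every death as a success, but the text supports only that deaths are unaddressed and may be scored so. A patient extubated for withdrawal of care and alive on the BAL day is plainly covered.

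A reader might also infer that intention-to-treat forces a classification for every patient. The documents explain the term only as analysis by assigned group.

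An effect as large as the margin is tempting too. It needs about 5 events in 51.5 patients (9.7 points), or 1 − (1 − 0.097)^(1/4) = 2.5% per day, above the range assumed here. Septic shock and moribund patients are excluded and everyone survives to day 5, so the number is probably small.

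The imbalance between arms is not certain. If therapy in the 4-day arm is extended and the BAL follows the actual end of treatment, that arm's window lengthens. The paragraph gives both a fixed day 5 and the day after treatment ends.

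Finally, live extubations between days 5 and 9 are also credited only to the 8-day arm and may matter more. With 5% to 40% extubated and p of 70% to 90% (assumptions), the artificial difference is 0.05 × 0.1 = 0.5 to 0.4 × 0.3 = 12 points. That is a separate problem. Solving it would not stop a withdrawal-of-care extubation from scoring as a response.

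**Conclusion.** The concern holds as a defect in a stated rule: withdrawal-of-care extubation counts as a microbiologic response, and death before the BAL may do so because it is not addressed. If BALs follow the scheduled days, the effect lies mainly in the 8-day arm and raises its response rate. The size cannot be taken from the documents. With hazards of 0.25% to 2% per day it is about 0.5 to 4 patients: at most 1 to 8 points against failure scoring, and 0.1 to 2.3 points against omission. The upper figures rest on the highest assumed hazard and on deaths being scored as responses. The direction is conservative for a claim that 4 days is non-inferior, so the risk is a distorted measure and a missed result rather than a false claim. The text does not support a stronger statement, whether that deaths are definitely scored as successes or that the bias reaches the margin.

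**What to change.** Amend the inference sentence so that MR is inferred only for patients who are alive and liberated from the artificial airway at the scheduled time, and not extubated for withdrawal of care. Then state how death and withdrawal are handled, in one of two ways:

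- classify them over a common window in both arms, for example through day 9, whatever each arm's BAL day; or
- report them as a separate category by arm, with sensitivity analyses that count them as non-response and that exclude them.

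They should not be scored as non-response only up to each arm's own BAL, because that turns the present bias into one favouring 4 days. The text should also say whether the BAL day moves when therapy is extended, and how a patient discharged alive before day 9 is treated, since follow-up ends at discharge.

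The cost is a few sentences. Mortality and ventilator days are already outcomes; the reason for extubation may need one added field. Blinding ends at treatment day 5, so that field should rest on a documented decision to withdraw care rather than a later judgement about recovery. Response rates will be slightly less favourable, and where these events count as non-response, some deaths unrelated to VAP will count against response.
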